Exclusion Criteria:

- Under 18 years old
- Does not speak English
- Unable to consent to involvement in the research study

- Is pregnant
- Has a bleeding disorder/diagnosis
- Currently taking anticoagulant medications and not stopped for procedure
- Documented low platelets (<100,000)
- Had a biopsy taken immediately prior to the endobronchial ultrasound

Sample Size Determination: A power analysis was conducted using a small to medium effect size (0.3), power of 0.8, and level of significance 0.05. It was determined that 44 patients would be needed in each group, for a total sample size of 88 patients. To allow for the possibility of removing participants from the final analysis due to missing data, we plan to enroll 120 patients (60 in each group).

- **Data Collection**

Before the study begins, information about the study will be provided to the providers and endoscopy team members, including information about the study purpose, inclusion/exclusion criteria, and procedures.

When a patient who meets the inclusion/exclusion criteria arrives for an appointment, a nurse from the study team will describe the study, answer any questions the patient has, and if the patient wants to enroll in the study, the study team nurse will review the information consent form. After the patient provides written informed consent, the nurse will remove the next envelope out of a box of prefilled and sealed opaque envelopes. The envelope will provide the Subject ID number to be used on all study-related documentation and the study Arm that the patient has been randomized to, either:

1. Cold saline group
2. Standard care group

These envelopes will be filled using a computerized simple random number generator (1:1 randomization) prior to the start of the study.

In addition to the group assignment, the envelope will include a data collection form. Data will be recorded directly on this form during the patient's visit. The form will collect the following information:

- Whether patient was assigned to the cold saline group or the standard care group
- Patient demographics including age, gender, current anticoagulant medications, current cancer diagnoses
- Temperature of cold saline (cold saline group only)
- Time cold saline placed (cold saline group only)
- Volume of cold saline used for irrigation
- Time each biopsy was obtained
- Number of biopsies
- Gauge of needle used to perform biopsy
- Type of suction used (i.e. slow-pull or 5mL, 10mL)

- Number of slides prepared

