To compare the effects of the intervention, a Chi Square test will be used to compare frequency of having to reperform biopsies among patients who received the cold saline irrigation compared to patients who did not receive the cold saline irrigation. A level of significance of $\alpha=0.05$ will be used.

- Hypothesis 3: Patients undergoing endobronchial ultrasound and biopsy who receive irrigation with cold saline prior to biopsy will experience a lower incidence of stopping the procedure without biopsy results compared to patients undergoing endobronchial ultrasound and biopsy who do not receive irrigation with cold saline prior to biopsy.

To compare the effects of the intervention, a Chi Square test will be used to compare frequency of stopping the procedure without biopsy results among patients who received the cold saline irrigation compared to patients who did not receive the cold saline irrigation. A level of significance of $\alpha=0.05$ will be used.

- Hypothesis 4: Patients undergoing endobronchial ultrasound and biopsy who receive irrigation with cold saline prior to biopsy will experience a lower incidence of requiring epinephrine to control bleeding after the biopsy compared to patients undergoing endobronchial ultrasound and biopsy who do not receive irrigation with cold saline prior to biopsy.

To compare the effects of the intervention, a Chi Square test will be used to compare frequency of epinephrine administration to control bleeding after the biopsy among patients who received the cold saline irrigation compared to patients who did not receive the cold saline irrigation. A level of significance of $\alpha=0.05$ will be used.

Interim data analysis will occur (1) once approximately 1/3 of the participants have been enrolled in each group and (2) once approximately 2/3 of the participants have been enrolled in each group. If interim calculations at time (1) or time (2) note a significant difference in outcomes between groups, data collection will be completed at that time and final analysis will be completed.

Ethical Considerations

- **Informed consent**

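### A significant result on one outcome can end data collection for all four hypotheses below 88 patients, so the stated 80% power need not hold for the others; the plan does not say which outcome triggers the stop

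*Combined protocol and SAP*

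**What the plan says.** Combined protocol and SAP, Participants, Sample Size Determination: "A power analysis was conducted using a small to medium effect size (0.3), power of 0.8, and level of significance 0.05". The result: "It was determined that 44 patients would be needed in each group, for a total sample size of 88 patients". Enrolment is raised to 120 (60 per group) as an allowance for missing data. The effect size is not tied to a named hypothesis, and no allowance is made for early stopping.

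Statistical Analysis gives each of the four hypotheses (unreadable slides, repeat biopsies, stopping without a result, epinephrine use) its own chi-square test at 0.05. None is named as primary. The last paragraph of that section sets looks at about 1/3 and 2/3 of enrolment per group. If either look should "note a significant difference in outcomes between groups, data collection will be completed at that time and final analysis will be completed". The triggering outcome, the number of outcomes needed and the significance level at the looks are not given. Nothing provides for continued data collection on hypotheses that did not trigger the stop.

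**The concern.** The power statement describes a trial that runs to 88 evaluable patients. The interim rule describes one that may end at about 40 or 80 enrolled, and both figures are below 88. The hypothesis that triggers the stop has its significant result. The others are tested on whatever has accrued.

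All four hypotheses predict benefit through one mechanism, less bleeding, so a true effect on more than one outcome is the case the plan expects. In that case an early stop on one outcome makes it more likely that a real benefit on another is reported as not significant. Peer-reviewed publication is planned, so such a result could be read as evidence of no effect.

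**Working it through.** **Inputs.** From the documents: effect size 0.3, power 0.8, alpha 0.05, 88 needed, 120 enrolled, 1:1 allocation, chi-square tests, four hypotheses, looks at about 1/3 and 2/3. Assumed, because the documents do not say: the effect size is Cohen's w, the between-outcome correlation is 0 to 0.6, and each truly improved outcome has w = 0.3.

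**1. The plan's own figure.** For a 1-df chi-square test, N = (z_0.975 + z_0.80)² / w² = (1.960 + 0.842)² / 0.09 = 87.2, rounded up to 88. This reproduces the plan. One-sided 0.05 gives (1.645 + 0.842)² / 0.09 = 68.7, which does not.

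**2. Power of a single test at each size** (noncentral chi-square, noncentrality N × 0.09):

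| N | Noncentrality | Power |
|---|---|---|
| 40 (look 1 of 120) | 3.60 | 47.5% |
| 80 (look 2 of 120) | 7.20 | 76.5% |
| 88 | 7.92 | 80.4% |
| 120 | 10.80 | 90.8% |

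If only 88 of the 120 are evaluable, the looks hold about 29 and 59 evaluable patients.

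**3. Power under the stopping rule.** Each outcome k is a running sum S_k(n) whose increments have mean 0.3 and variance 1 per patient, with correlation ρ between outcomes, and Z_k = S_k/√n. The trial stops for all outcomes at the first look that meets the trigger. Each hypothesis is then judged by |Z_k| > 1.96 on the data at the stop (200,000 runs per setting). Ranges are for ρ from 0 to 0.6.

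| Trigger | Truly improved | 88 evaluable (looks 29/59/88) | 120 evaluable (looks 40/80/120) |
|---|---|---|---|
| No early stop | any | 80% | 91% |
| Any one outcome, p<0.05 | two tested, both | 61–68% | 67–75% |
| Any one outcome, p<0.05 | two of four tested | 59–65% | 65–72% |
| Any one outcome, p<0.05 | all four | 45–56% | 52–63% |
| Any one outcome, p<0.05 | one of four tested | 76–79% | 85–87% |
| Hypothesis 1 only | all four: Hypothesis 1 | 84% | 92% |
| Hypothesis 1 only | all four: each of the other three | 59–66% | 66–74% |
| All four significant | all four | 81–82% | 91–92% |
| O'Brien-Fleming-type, any one outcome | two tested, both | 72–77% | 81–87% |
| O'Brien-Fleming-type, any one outcome | all four | 64–73% | 73–83% |

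The O'Brien-Fleming-type rows assume two-sided trigger levels of 0.0005, 0.014 and 0.045, with the other outcomes tested at the plan's 0.05 when the trial stops.

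With two improved outcomes, 120 evaluable and the p<0.05 trigger, 62–73% of trials stop at the first look. With the O'Brien-Fleming-type trigger about 10% do.

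**4. Cross-check on binary data.** Four outcomes with w of about 0.3, Pearson chi-square and latent correlation 0 to 0.5 give 45–51% at 88 and 52–57% at 120, in line with the all-four row.

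**The case against.** The strongest objection is that the trigger is undefined. If the rule means that all four outcomes must be significant, power per hypothesis stays at 81–82% (88 evaluable) or 91–92% (120), and nothing is lost. This stands as a limit on the finding, but nothing in the text requires that reading, and the ambiguity is itself a defect.

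The loss also depends on two or more real effects. With one improved outcome and all 120 evaluable, power is 85–87%. The plan attaches its 80% to no particular hypothesis and does not promise it for all four jointly. That stands too, although the four hypotheses as written all predict benefit.

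Three stronger readings are tempting:

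- A reader might infer one power figure that applies to every hypothesis. The documents give neither the number of true effects, nor their correlation, nor event rates, so only ranges under stated assumptions can be defended.
- A reader might compare a trial running to 120 with a fixed 88. The plan describes the extra 32 as a missing-data allowance, so the fair pairs are 88 against 80% and 120 against 91%.
- A reader might infer that the loss persists in full whatever significance level is used at the looks. The documents do not support this, because they set 0.05 for each hypothesis test. With an O'Brien-Fleming-type trigger and the other outcomes tested at 0.05, two improved outcomes with 120 evaluable give 81–87%. Only if the other outcomes are also held to the strict level of the stopping look does this fall to about 69–75%.

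**Conclusion.** The point holds conditionally. The 80% is a fixed-sample figure, and the interim rule can end the trial before the sample it rests on. If any one outcome can trigger the stop and at least two outcomes truly improve with w = 0.3, power per improved outcome falls about 16 to 39 percentage points below the matching fixed design (91 − 75 = 16 and 91 − 52 = 39 at 120; 80 − 68 = 12 and 80 − 45 = 35 at 88, so 12 to 35 there). If only Hypothesis 1 triggers, it keeps its power and the other three lose it. If all four must be significant, there is no shortfall. A stricter interim level reduces the loss without always removing it: with four improved outcomes and 88 evaluable, power is still 64–73%. The w metric, the correlations and the number of improved outcomes are assumptions. The plan should be changed, but nothing here makes the trial unworkable.

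**What to change.** In the interim paragraph of Statistical Analysis, name the outcome or outcomes that can trigger a stop. Add that significance on one outcome does not end data collection for the other hypotheses before 88 evaluable patients. Naming a single trigger is not enough alone, as the Hypothesis 1 rows show.

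The cost is the option to stop early for benefit, which is lost or narrowed: as scheduled, both looks fall below 88. No patients beyond the planned 120 are needed.

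If stopping on any outcome is kept, make two changes instead:

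- In Sample Size Determination, state that 80% applies only if the trial runs to 88 evaluable patients. Give the lower power under the stopping rule, with the number of improved outcomes, the correlation and the evaluable N that it assumes.
- In Statistical Analysis, state that hypotheses not significant at an early stop will be reported as inconclusive, not as showing no difference.

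This alternative costs only wording and a less favourable power figure.
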